mechanistic interest is in capturing changes in brain function and pain modulatory balance induced by the interventions. Thus, this research includes aspects of Stage 0 (basic science to inform intervention development) and Stage 1 (modification and refinement of existing interventions) intervention development (50). Subjects. A total of 360 individuals with knee OA (180 AA, 180 NHW) will be enrolled in the study. We anticipate a 10% attrition rate, given the brief duration of the intervention, which will yield a final sample size of at least 320 participants. In our pilot trial of tDCS, attrition was much lower (2.4%)(4); however, in this larger two-site study, we account for the possibility of increased attrition. As during the current funding cycle, both community-based and clinic-based recruitment methods will be utilized at both study sites with similar inclusion-exclusion criteria as in our prior and ongoing work. Initial Screening. All participants will undergo a knee OA screening interview that shows 87% specificity and 92% sensitivity for detecting knee OA (51). The screening will also assess demographic and health history information to ensure that no exclusion criteria are present. Eligible individuals will be scheduled for baseline assessment at the study site. Demographic Measures. Ethnic group will be determined by participant self-report using the standard Health and Human Services categories. We will recruit adults who self-identify as either Black/African American or non-Hispanic white (NHW) as their primary ethnic/race group. Socioeconomic Status (SES): Because ethnic/race groups often differ in SES (52), and lower SES has been associated with increased risk of clinical pain (53, 54), including increased prevalence of arthritis (55, 56), we will obtain measures of SES.

D2.1. Baseline Assessment: Two baseline visits will occur in the six weeks before the intervention. The first baseline session will assess: health history, cognitive function, clinical pain and function and QST measures. The second baseline session will involve brain imaging. In order to distribute participant burden, some questionnaires will be completed online between the first 3 sessions, while others will be completed during the two pre-treatment sessions. The following questionnaires will be completed during the pre-treatment phase of the protocol.

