
We recognize that scheduling five daily visits is a challenge, and we expect missed visits for some participants. If participants miss only one of five visits, that will not be considered a protocol deviation; however, if they miss two or more visits, this will be reported as a minor deviation.

Additional Post-Treatment Measures: We will assess the following measures post-treatment. 1) Side Effects: Participants will complete a brief questionnaire assessing side effects of treatment, including side effects that can occur with tDCS (e.g. tingling, itching, headache, fatigue) or mindfulness (breathing changes, dizziness, sleep changes, anxiety). And participants will be asked whether they believe they received real or sham tDCS. 2) Treatment Satisfaction/Helpfulness: Participants will provide a rating of overall satisfaction with treatment, and a rating of how helpful they found the treatment for reducing their pain. 3) Three-Month Follow-Up: Each month for three months post-intervention, participants will complete a follow-up questionnaire, including the NRS assessing average pain over the past 24 hours, as well as ratings of pain interference and mood. We will also administer the PSS and the PCS at these follow-up time points. At the final follow-up assessment, we will ask participants to report on their global impression of treatment helpfulness and to indicate

whether and how often they continue to use their BAT skills. 4) **Debriefing:** After the final follow-up assessment, one of the research team members will telephone the participant to explain the purpose of the study. At this time, we will not be able to reveal which tDCS group they were in, as the investigators will remain blind to this. In addition, we will not reveal which BAT condition they received, because if participants communicate such information to others who are in the study, this could bias study results. Interested participants will be directed to online resources to learn more about mindfulness.

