D3. Data Analysis: Sample Size and Statistical Power: In this study, we are proposing to randomize 360 individuals to four groups defined by a 2X2 factorial design, and we expect to have 320 completers. Table 4 illustrates the effect sizes (Cohen's D) produced by the proposed interventions compared to their sham conditions for different outcomes that have been reported in our previous studies (4, 5). We plan to conduct six primary hypothesis tests (Sham vs Real BAT and Sham vs. Real tDCS for three primary outcomes) with the use of F-test at a corrected $\alpha=0.0083$ significance level. Even with this conservative approach, we have sufficient power for detecting single intervention effects, with power greater than 90% for most outcomes. We do not have effect size estimates for the

combined effect, but our sample size provides 80% power to detect effects as small as Cohen's $D=0.39$.

Table 4: Effect Sizes Observed for tDCS and MMT in our Previous Work				
		Power for Different Sample Sizes		
Outcome	Cohen's D	N = 300	N = 320	N = 340
tDCS (from Ahn, et al)				
CPM	0.34	0.61	0.65	0.68
Pain Rating	0.44	0.88	0.90	0.92
MMT (from Zeidan, et al)				
Heat Pain	0.51	0.97	0.98	0.99
rCBF	0.82	0.99	0.99	0.99

Statistical Analysis Plan:

Summary statistics will be calculated by group for demographic characteristics and all predictor and outcomes measures at baseline and follow-up. Statistical inference will be conducted for the three primary aims as follows.

For **Aim 1**, we will test the effects of BAT, tDCS, and their interaction upon outcomes. For hypotheses 1a-1c, our primary outcomes will be pain modulatory balance (ratio of CPM to temporal summation), pain-evoked cerebral activation, and clinical pain, respectively. Intention-to-treat analysis will be conducted using appropriate linear contrasts to test for intervention effects accounting for interaction terms based on general linear models with covariate adjustment for site, sex, age, and baseline value. Specifically, for each outcome (Y), the model will be:

$$E(Y) = \beta_0 + \beta_1 \text{BaselineScore} + \beta_2 \text{Covariates} + \beta_3 \text{BAT} + \beta_4 \text{tDCS} + \beta_5 \text{AA} +$$

$$\beta_6 \text{BAT} * \text{tDCS} + \beta_7 \text{BAT} * \text{AA} + \beta_8 \text{tDCS} * \text{AA} + \beta_9 \text{BAT} * \text{tDCS} * \text{AA},$$

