where BAT and tDCS are dummy variables for interventions, AA is the dummy variable for African Americans. Linear contrast will be employed to test the main effect of BAT (corresponds to the test of $\beta_3 + \beta_6/2 + \beta_7/2 + \beta_9/4=0$) and tDCS (test of $\beta_4 + \beta_6/2 + \beta_8/2 + \beta_9/4=0$). These six tests (2 main effects for three primary outcomes) will be performed at one-sided $\alpha=0.0083$ significance level. In addition, point estimates and 95% confidence intervals will be obtained for the BAT and tDCS effects with or without the presence of the other treatment in the whole population or within AA and NHW subgroups. We will use normal probability plots to assess distributional assumptions of the models. The above analysis plan will be followed for other outcomes including resting state cerebral blood flow, disability and functional performance, as well as the analysis of changes of the outcomes from post-treatment to three-month follow-up.

For **Aim 2**, we will assess interactions between race and intervention. Point estimates and 95% confidence intervals will be obtained for the race difference in the effects of BAT and tDCS on each outcome. Because we expect the interaction effect to be smaller than the main effect, for formal hypothesis testing, we plan to pool evidence across three primary outcomes to test the ethnic group differences. Specifically, we will obtain a p-value corresponding to test the hypothesis $\beta_7=\beta_8=\beta_9=0$ for

each outcome based on the general linear model specified in the analysis plan for Aim 1. And Fisher's combination of three p-values will be used as the overall test statistic, which will be compared to the null distribution obtained through permutation of ethnic group variable.

For Aim 3, path models with strictly ordered relationships will be used to study the interventions' direct effects on clinical pain and disability and the indirect effect on the mediating variables including pain modulatory balance; resting state and stimulus-evoked pain-related brain function; perceived stress, pain catastrophizing, and mindfulness. We will construct additional analyses using pre-treatment variables as predictors of intervention effects. We will examine separate multivariable models for each ethnic group to determine whether mediators of treatment effects differ for AAs vs. NHWs.

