Missing Data and Sensitivity Analysis: The four randomized groups will be compared in missing patterns in the primary outcomes including reasons for missing data, timing of missing data, and distributions of baseline covariates and earlier outcomes.

We will consider the following approaches to impute each of the primary outcomes: (1) the last-observation-carried-forward method; (2) missing primary outcome predicted by a fitted regression model using demographic and baseline clinical variables; (3) missing primary outcome predicted by baseline and available follow-up outcomes on a fitted regression model. The imputation method for the primary intent-to-treat analysis will be selected using cross-validation performed on the participants with complete data. Specifically, we will evaluate imputation accuracy based on 2,000 repetitions that randomly leave out 20% of the complete samples. In addition, to consider the uncertainty due to missing values, we will apply the SAS multiple imputation procedure to generate multiple imputed data sets using the selected imputation approach, and combine results from analyses of these data sets, e.g., to provide mean and variance of the treatment effect estimates. No imputation is planned for secondary outcomes. Missing data in secondary outcomes will be considered missing. For a subject to achieve a given secondary endpoint, that endpoint must be observed.

7. Possible Discomforts and Risks:

Potential risks are minimal and relate primarily to short-term discomfort of the sensory testing procedures delivering cold and mechanical pressure. The risks from brain imaging procedures are thought to be minimal in appropriately screened participants. Questionnaires include specific questions about how a participant feels and ask the participant to think about life experiences. Reading or answering these questions may cause some participants embarrassment or discomfort.

Potential Risks

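### The month-3 analysis appears to drop anyone missing month 3, although months 1 and 2 were collected, and the missing-data rule for follow-up pain is unstated

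*Combined protocol and SAP*

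**What the plan says.** - **Model.** Under Aim 1 of the Statistical Analysis Plan (section D3): "Intention-to-treat analysis will be conducted using appropriate linear contrasts". The model printed there has one outcome value and one baseline score per person. It has no time term and no random effect.
- **Extension to follow-up.** The end of the Aim 1 text applies the same plan to other outcomes, "as well as the analysis of changes of the outcomes from post-treatment to three-month follow-up".
- **Missing data.** The section on missing data and sensitivity analysis gives the primary outcomes three candidate imputation methods, one of which uses available follow-up values, and then multiple imputation. For the rest: "No imputation is planned for secondary outcomes. Missing data in secondary outcomes will be considered missing". It adds: "For a subject to achieve a given secondary endpoint, that endpoint must be observed". The comparison of missing-data patterns between groups is also limited to the primary outcomes.
- **Data collected.** From the additional post-treatment measures, item 3: "Each month for three months post-intervention, participants will complete a follow-up questionnaire". It covers average NRS pain, pain interference, mood, the PSS and the PCS. The D1 overview gives the purpose of follow-up as assessing whether effects persist.
- **Expected loss.** From D2: "We anticipate a 10% attrition rate, given the brief duration of the intervention". No separate rate is given for the three months after treatment.

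**The concern.** A model with one value per person has no place for the month 1 and month 2 answers of someone who is missing at month 3. With no imputation, that person leaves the month-3 analysis. If people stop answering because their pain has returned, those who remain are a selected group, and the comparison describes them rather than everyone randomised. The values that would reveal and largely correct this selection have already been collected.

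Two gaps in the text make it harder to know what will be done. Clinical pain is a primary outcome, but follow-up clinical pain is never labelled primary or secondary, so either missing-data rule could apply. And for a change from post-treatment, the plan does not say whether the baseline score in the model is the pre-treatment or the post-treatment value. That choice affects the size of any bias.

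At stake is the evidence on persistence. The 10% attrition figure is justified by the short intervention and gives little assurance about three further months of online or telephone questionnaires.

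**Working it through.** **1. The plan's own figures.** Inputs from D3: 360 randomised, 320 completers expected, d = 0.44 for the tDCS pain rating, alpha 0.0083, stated power 0.90. For a factorial main effect with N/2 per level, the noncentrality is d x sqrt(N/4) = 0.44 x sqrt(80) = 3.94. At two-sided 0.0083 the normal approximation gives power 0.902 and the noncentral t gives 0.899, so 0.90 is reproduced. For attrition, 360 x 0.90 = 324, which fits at least 320.

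**2. Sample size if month-3 loss is higher.** The loss rates are assumptions. The same test is used only as a yardstick, because the 0.0083 level belongs to the primary tests.

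| Loss | N observed | Power at d = 0.44 |
|---|---|---|
| 10% | 324 | 0.90 |
| 20% | 288 | 0.86 |
| 30% | 252 | 0.80 |

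**3. Bias in the month-3 level.** Assumptions, none given in the documents except the effect size: constant true effect 0.44 SD; baseline to follow-up correlation 0.5; correlation between months 0.60 or 0.75; dropout after months 1 and 2 driven by the last pain score, with probit slope 0.5 to 1.5 and the same slope in both arms. Observed-case ANCOVA at month 3, pooling two independent large simulations (400,000 participants per scenario):

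| Loss | Estimate | Shrinkage, (0.44 - estimate)/0.44 |
|---|---|---|
| 10% | 0.390 to 0.428 | 3% to 11% |
| 20% | 0.363 to 0.422 | 4% to 18% |
| 30% | 0.345 to 0.419 | 5% to 22% |

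Across all the set-ups tried, the range is roughly 1-24%. Using the month 1 and 2 values returns 0.433 to 0.446. The cause is simple: when treatment works, the same dropout slope removes more sham participants (about 25% against 14% at 20% loss and slope 1.5).

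**4. Bias in the analysis the plan names.** A post-treatment value was added, equally correlated (0.60 or 0.75) with each month.
- Change from post-treatment, adjusted for pre-treatment baseline only: bias about 0. With equal correlations r, the covariance of (month 3 - post-treatment) with month 1 or month 2 is r - r = 0, so selection on those months does not move the change. This depends on the equal-correlation assumption.
- Change also adjusted for the post-treatment value: about 0.002-0.02 SD. If dropout depends on pain in one arm only: about 0.02-0.11 SD.

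**5. No true effect.** With the same slope in both arms, bias in the level is within 0.007 SD. At roughly 20% loss (within-person correlation 0.5 to 0.7, logistic slope 0.7), it is 0.035-0.045 SD if dropout depends on pain in one arm only, and about 0.07-0.08 SD if it runs in opposite directions by arm. With the earlier months used, the bias is 0.003 SD or less. The standard error is about 0.08-0.11 either way, so the gain is mainly in bias and little in precision.

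**The case against.** The strongest reply is that the large percentages belong to a comparison of month-3 levels, whereas the plan names change from post-treatment, for which the bias is near zero or small. That stands. A reader might infer that the trial's persistence result will be attenuated by up to a quarter; the documents do not support this.

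Other parts of the reply also stand:
- The top of the range needs severe dropout. Slope 1.5 with 30% loss means that someone 2 SD worse has about an 89% chance of leaving at each dropout point, against 0.05% for someone 1 SD better. Nothing in the documents suggests this.
- The simulated dropout is missing at random given the monthly values, so recovery by a method that uses them is built in.
- It is tempting to say that earlier monthly data certainly go unused. That is an inference from the model and the no-imputation rule. The protocol's heading for three-month follow-up covers all three monthly assessments, so months 1 and 2 may be analysed too.
- It is tempting to read "For a subject to achieve a given secondary endpoint, that endpoint must be observed" as scoring missing values as failures, in conflict with the sentence before it. It can equally restate that nothing is imputed, and for continuous scores it has no effect.
- Observed-case analysis is not biased in every case, as step 5 shows. The intention-to-treat label reaches these outcomes only by cross-reference.
- The trial describes itself as proof of principle and not an efficacy trial.

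What the reply does not answer is that no repeated-measures model is named for outcomes collected monthly by design, and that the rule for follow-up pain is left open.

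**Conclusion.** The point holds in a limited form. On the natural reading, a participant missing month 3 drops out of the month-3 analysis despite having month 1 and 2 values for NRS pain, the PSS and the PCS, and the missing-data rule for follow-up clinical pain is unspecified.

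Under the stated assumptions, the harm is a shrinkage of roughly 1-24% only if month-3 levels are compared. For change from post-treatment it is about 0 or about 0.002-0.02 SD, depending on which value is adjusted for. The second figure rises to about 0.02-0.11 SD if dropout depends on pain in one arm only. The near-zero result relies on equal correlations over time, and loss rates and dropout mechanisms are not given in the documents.

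The unused monthly data concern only the questionnaire measures. QST, imaging and the SPPB have a single post-treatment assessment. The six primary tests are unaffected. This is a cheap improvement of modest importance.

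**What to change.** In the Statistical Analysis Plan:
1. For questionnaire outcomes measured at months 1-3, replace the single-time-point observed-case model with a likelihood-based mixed model for repeated measures. Use all observed monthly values, an unstructured covariance, the same covariates and arm-by-month terms, and read off the month-3 contrast.
2. Include the post-treatment value where the same instrument was used. This needs checking for the NRS: treatment visits ask about current pain, follow-up about the 24-hour average.
3. State which missing-data rule covers follow-up clinical pain, and, wherever change from post-treatment is still analysed, which value serves as the baseline score.
4. Do not extend multiple imputation to imaging outcomes in participants who have no scan by design. The protocol plans imaging in only about two-thirds of the sample.

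The cost is SAP wording and slightly more analysis work, with no new data. The mixed model assumes data are missing at random given the observed monthly values. It does not protect against dropout driven by pain that was never recorded.
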